1.0 Purpose and Objectives

1.1 Purpose

3

4

13

21

22

23 24

25

26

30

34

35

- 5 This prospective randomized controlled trial evaluates the feasibility of using percutaneous peripheral nerve
- 6 stimulation (PNS) to reduce acute post-surgical pain in nontraumatic lower extremity amputation and
- 7 decrease the incidence and/or severity of chronic phantom limb pain (PLP) or residual limb pain (RLP).
- 8 The use of a novel, intentionally reversible, single-lead, PNS system has demonstrated promising results in
- 9 the management of chronic pain syndromes including PLP and RLP (7). This study will apply the same
- 10 PNS system to nontraumatic transferoral or transtibial amputees (TFA or TTA, respectively) in the post-
- operative setting within 5-7 days after surgery to evaluate the feasibility and efficacy of peripheral nerve
- stimulation in the management of acute and chronic PLP and RLP.

1.2 Objectives

- 14 The goal of this study is to demonstrate that PNS is a safe, effective method of reducing acute and chronic
- pain in the nontraumatic lower extremity amputee, and can lessen the use of opioid pain medications. This
- pilot study will evaluate the feasibility of recruitment, randomization, retention, assessment procedures,
- and implementation of PNS in the acute post-operative period to develop a larger, multicenter, blinded,
- placebo-controlled, randomized clinical trial to evaluate efficacy in reducing acute and chronic PLP and
- 19 RLP. Upon completion, we will assess the reliability and validity of the proposed study design. In
- 20 conducting this investigation, we hope to answer the following questions:
 - What is the feasibility of placing a PNS system in a transfemoral or transtibial amputee in the acute post-operative period?
 - Does PNS produce clinically significant reductions in acute PLP or RLP?
 - Does the application of PNS in the acute post-operative period reduce the incidence and severity of chronic PLP and RLP?
 - Can PNS lessen the use of opioid and non-opioid pain medications?
- Does PNS affect time to prosthesis fitting, function outcomes (Functional Independence Measure [FIM] scores), wound healing, incidence of neuromas, time to hospital discharge, 30-day readmission rate, and hospital discharge survey answers?

1.3 Study Hypothesis

- 31 Percutaneous peripheral nerve stimulation may provide clinically significant relief of acute post-surgical
- 32 pain in nontraumatic lower extremity amputation and decreases the incidence and/or severity of chronic
- 33 PLP and RLP when applied in the acute post-operative setting.

2.0 Background and Significance

2.1 Background

- 36 Amputees commonly experience acute and chronic post-amputation pain. Amputation leads to persistent
- pain in up to 70-90% of patients, resulting in decreased quality of life, increased risk of depression, and
- 38 negative impacts on interpersonal relationships and ability to work (10). The prevalence of persistent PLP
- or RLP in amputees is estimated to range from 45 to 74% for RLP and 51 to 85% for PLP (11, 12). Pain
- 40 secondary to loss of limb, rather than the loss of limb itself, has a larger effect on ability to perform activities
- of daily living, complete simple tasks, and shows a negative correlation with return to work (13). Post-
- 42 amputation pain can also impact the ability to use a prosthesis.
- When present, post-amputation pain is difficult to manage. More than 50 different treatments have been
- developed for PLP, yet most have been unsuccessful (1). In many studies, acute PLP intensity was the only

significant independent predictor of chronic PLP intensity at 6 and 12 months after amputation (2). Liu et al have demonstrated the most significant risk factor for post-procedure pain (PPP) for total knee and total hip arthroplasties to be acute postoperative pain (3). Increased postoperative Visual Analog Scale (VAS) scores on days 1 to 5 has correlated with PPP at 3 months (4).

Perioperative pain management in lower extremity amputations commonly involves a multimodal approach utilizing pharmacologic and interventional therapies (8). Both acute and persistent post-amputation pain is commonly managed with opioids which are associated with undesirable adverse effects such as nausea, vomiting, sedation, and respiratory depression. Further, they often result in unsatisfactory reductions in post-amputation pain and have the potential for addiction and misuse (14). Several interventional therapies are available for use in the perioperative setting, however there is no consistent therapy that has been shown to prevent the development of persistent post-amputation RLP or PLP (8). Karanikolas et al demonstrated that optimized epidural analgesia and/or intravenous patient-controlled analgesia (PCA) in the perioperative setting decreases PLP intensity, prevalence, and frequency at 6 months after amputation (23). This study did not assess sustained pain relief beyond 6 months, and RLP was not significant in the study population.

Peripheral nerve catheter based pre-emptive analgesia has become an essential component of Standard Medical Therapy (SMT) at the Hunter Holmes McGuire VA Medical Center (VA) in lower extremity amputations to prevent onset of chronic pain, decrease opioid use, and decrease health care utilization (both inpatient and outpatient). The efficacy of peripheral nerve catheter-based regional analgesia for pain relief in the immediate postoperative period is well documented. However, associated motor, sensory, and proprioceptive deficits can increase the risk of falling (15) and duration of use is limited due to risk of infection (16). This intervention is limited by the fact that peripheral infusion catheters (typically femoral and sciatic nerve catheters) must be removed by postoperative day 5 to reduce the risk of infection. Furthermore, Apfelbaum demonstrated in a large study that many patient's worst incidence of postoperative pain occurs after discharge (5). Given this safety limitation and the need for continued pain control in the entire perioperative period, this study seeks to augment this therapy with a percutaneously placed PNS system. This is expected to extend the period of perioperative pain control to greater than 30 days and beyond. There is convincing evidence in studies thus far showing that when a PNS system is applied to chronic pain sufferers, it can extend the treatment effect well beyond the time in which it is implanted. To date, the system studied is the only intentionally reversible, percutaneously placed PNS system. More comprehensive and earlier treatment of acute pain is believed by many in the field to be even more effective (6,7).

2.2 Literature Review

PNS has been studied for the treatment of some chronic pain syndromes (7, 17-19), including persistent post-amputation pain. The mechanism of action of peripheral nerve stimulation in pain relief is commonly explained using the "gate control theory" of Melzack and Wall (20). This theory explains that electrical current-induced activation of large-diameter myelinated afferent peripheral nerve fibers inhibits the transmission of pain signals from small-diameter pain fibers to the central nervous system at the level of the spinal cord (15). Rauck et al (7) showed that 9 of 14 subjects who completed two-weeks of PNS therapy reported reductions in mean daily worst post-amputation pain, average RLP and PLP, and interference from RLP and PLP at least one month after the end of treatment. Interference from RLP or PLP refers to how pain has interfered with general activity, mood, walking ability, work, relations with others, sleep, and enjoyment of life. PNS was shown to be effective in reducing post-amputation pain when most pain is confined to one or two nerve distributions (7, 21-22). Results showed that 14 of 16 subjects reported ≥75% paresthesia coverage from PNS, obtained clinically significant pain relief, and proceeded to a 2-week home trial with this system. 9 subjects completed the 2-week trial and 5 subjects did not complete the trial because

- of accidental dislodgement (N=2), temporary discomfort near the lead (N=2), and return of post-amputation
- 91 pain despite stimulation (N=1). The 9 responders who completed the home trial reported reductions in their
- mean daily worst post-amputation pain ($56 \pm 26\%$, $56 \pm 26\%$, N = 9), average residual limb pain ($72 \pm 26\%$)
- 93 28%, $42 \pm 27\%$, N = 7), average phantom limb pain $(81 \pm 28\%, 47 \pm 48\%, N = 7)$, interference from residual
- 94 limb pain $(81 \pm 27\%, 53 \pm 17\%, N = 6)$, interference from phantom limb pain $(83 \pm 31\%, 56 \pm 46\%, N =$
- 95 7), and Pain Disability Index (PDI) $(70 \pm 38\%, 55 \pm 32\%, N = 9)$ during the 2nd week of stimulation and 4
- 96 weeks after the end of stimulation, respectively. All 9 responders rated their change in quality of life as
- 97 improved at the end of stimulation and at the end of the 4-week follow-up period.

3.0 Scientific Rationale and Study Design

3.1 Scientific Rationale

- The feasibility of using PNS to reduce acute postoperative pain is not currently well documented in medical
- literature. A preliminary report demonstrated the use of PNS to treat pain after total knee arthroplasty in
- 102 10 subjects who experienced postoperative knee pain difficult to control with oral analgesics between 6 and
- 97 days after surgery. Nine out of 10 subjects experienced at least 57% decrease in pain, and half had
- 104 complete resolution of pain at rest (9). The application of PNS in the treatment of acute postoperative
- amputation pain and the efficacy of using PNS to prevent or reduce the severity of persistent PLP or RLP
- has not been documented.

98

99

115

128

- 107 Currently, literature documenting the use of PNS in postoperative amputation pain is limited. The PNS
- system in this study has been used previously to evaluate the reduction in chronic post RLP or PLP (7).
- There is an ongoing multi-site investigation evaluating the use of PNS in chronic pain after traumatic lower
- extremity amputation. To date, there is no study that documents the use of PNS therapy in the acute
- postoperative period after TFA or TTA. This study aims to report on the feasibility and efficacy of using
- PNS in this clinical setting to evaluate reductions in acute post-amputation pain, incidence or severity of
- chronic post-amputation pain, and reliance on opioid medications amongst other outcome measures as
- described in Section 4.0: Study Outcomes and Exploratory Measures.

3.2 Study Design

- This prospective randomized controlled trial aims to assess the feasibility of using a novel percutaneous
- peripheral nerve stimulator system to produce clinically significant reductions in acute post-surgical pain
- after nontraumatic lower extremity amputation, and evaluate reductions in the incidence and/or severity of
- chronic PLP or RLP. Subjects who have moderate pain 2 to 7 days after transfemoral or transibial
- amputation surgery will be enrolled and randomized to Group 1 ("Treatment Group") or Group 2 ("Control
- Group"). Subjects in Group 1 will be treated with 30 to 60 days of PNS in addition to SMT. Subjects in
- Group 2 will be treated with the SMT alone. SMT is defined as the same routine medical care given to all
- patients, regardless of whether they are enrolled in the study. This may include, but is not limited to non-
- opioid and opioid pain medications, regional anesthesia peripheral nerve blockade, daily postoperative
- visits by the Acute Pain Service, and follow-up appointments in the Interventional Pain Clinic.
- Group 1: 30 to 60 days of peripheral nerve stimulation starting within 7 days after surgery and Standard Medical Therapy
 - Group 2: Standard Medical Therapy only
- Subjects are evaluated daily by study investigators from the time of study enrollment to hospital discharge.
- 30 Subsequent telephone or outpatient clinic evaluations occur at intervals which are detailed in the Schedule
- of Study Procedures (Appendix).

4.0 Study Outcomes and Exploratory Measures

4.1 Primary Outcomes

4.1.1 Effect of PNS on acute pain after lower extremity amputation

The Brief Pain Inventory Short Form (BPI) is a 9-item questionnaire used to evaluate the severity of a patient's pain and the impact of this pain on the patient's daily functioning. The patient is asked to rate their worst, least, average pain, and rate the degree that pain interferes with general activity, mood, walking ability, normal work, relations with other persons, sleep, and enjoyment of life on a 10-point scale. Levels of PLP and RLP are re-assessed at follow-up Visits according to the Schedule of Study Procedures. Questions used to assess pain or sensation are listed below. For BPI #3, #4, and #5, responses are recorded on an 11-point scale from "0" to "10" with "0" defined as "No Pain" and "10" defined as "Pain as Bad as You Can Imagine."

- Check yes or no if you experienced any (phantom limb or residual limb) sensation in the last 24 hours
- BPI #3: "Please rate your (phantom limb or residual limb) pain by marking the box beside the number that best describes your pain at its **worst** over the last 24 hours."
- BPI #4: "Please rate your (phantom limb or residual limb) pain by marking the box beside the number that best describes your pain at its **least** over the last 24 hours."
- BPI #5: "Please rate your (phantom limb or residual limb) pain by marking the box beside the number that best describes your pain on the **average** over the last week."

4.1.2 Effect of PNS on the incidence and severity of chronic pain after lower extremity amputation

Chronic pain (i.e. pain persisting for more than 2 to 3 months after TFA or TTA surgery will be evaluated using BPI questions #3, #4, and #5 as above at follow-up Visits according to the Schedule of Study Procedures. Data will be compared between groups to assess for differences in the incidence and severity of chronic pain.

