5.5.6 Visit 7, 8, and 9: Weekly follow-up telephone evaluations

Visits 7, 8, and 9 consist of weekly telephone evaluations at 5, 6, 7 weeks after starting peripheral nerve stimulation (Group 1) or discontinuation of peripheral nerve block (Group 2). If issues related to the

peripheral nerve stimulator device or leads occur that cannot be resolved by telephone, subjects may be evaluated in the Interventional Pain Clinic if needed.

Subjects are asked to rate their worst, least, and average PLP and RLP (BPI #3, #4, and #5). A medical reconciliation will be completed during each phone evaluation by asking the subject how many pills of narcotic pain medications they have left and querying the Virginia Prescription Monitoring Program Database.

5.5.7 Visit 10: Second outpatient clinic evaluation / up to 60 days after start of PNS

All subjects are asked to return to the Interventional Pain Clinic at approximately 60 days after starting peripheral nerve stimulation (Group 1) or discontinuation of peripheral nerve block (Group 2). Stimulator leads will be removed by gentle traction. The lead will be visually inspected by study staff to evaluate for lead fracture. In the case of a retained lead fragment, study staff will determine the most appropriate medical plan to further evaluate and treat the subject. In most instances, retained lead fragments do not need to be removed and are rarely associated with further complications. Lead exit sites are inspected for skin irritation, infection, and inflammation. Both groups will continue to be treated with SMT as needed until the end of participation in the study. Subjects in Group 1 are encouraged to complete the entire 60-days of peripheral nerve stimulation, however are free to discontinue treatment at any time during the treatment phase.

5.5.8 Visits 11, 12, and 13: Phone evaluations at 3, 6, and 12 months after study enrollment

Telephone evaluations for both groups occur at approximately 3, 6, and 12 months after study enrollment. Outcome measures to be assessed are listed in the Schedule of Study Procedures.

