6.3 Data Analysis

A table of outcome measures recorded during the study can be found in Appendix. Scores rating daily 491 492 average, worst, and least pain will be compared between groups. Changes in pain will be evaluated for

individual subjects and compared between groups. For each subject, mean pain scores over the first and 493

494 second months following TFA or TTA surgery will be calculated. An overall mean across all subjects will

be calculated. Additionally, sub-analyses will be performed to determine if there is a difference in these 495

outcomes between groups over different post-operative phases (such as acute (e.g. days 1-30) or subacute 496

497 (e.g., 1-3 months), or chronic (e.g. >3 months)). Statistical analysis will be performed with two-sample t-

498 test, and p-values will be reported without adjustment, consistent with feasibility study design and the

499 number of subjects.

500 Pain medication usage will be recorded in subject diaries and obtained during follow up encounters. Opioid

medication use will be analyzed by averaging 24-hour morphine equivalent dosing (MED) over each 501

502 follow-up interval and comparing groups. Changes in opioid medication use will be reported for individual

503 subjects by calculating morphine equivalent dosing (MED). Average MED will be calculated and compared between groups. The time to cessation of opioid use will be reported. Side effects associated 504

with opioid use will be assessed at each visit and the number of side effects occurring over various intervals 505

506 will be recorded. Analgesic-related outcomes will be compared between the Groups.

507 Patient Global Impression of Change (PGIC), Pain Catastrophizing Scale (PCS), and Pain Disability Index

508 (PDI) scores will be averaged for each group and compared. Data regarding functional outcomes

509 (Functional Independence Measure [FIM] score), time to wound healing, incidence of neuromas, prosthesis

fitting, time to hospital discharge, 30-day readmission rate, and hospital discharge survey will be compared 510

between groups. 511

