10.0 Appendix

Schedule of Study Procedures

									Meds/SE Pain/Sense								Sti	udy F	roce														
Incidence of neuromas	30-day readmission rate	Hospital discharge survey	Time to hospital discharge	Time to prosthesis fitting	FIM	PDI	PCS	PGIC	BPI-9 (interference)	Pain medications	Opioid-related side effects	Phantom sensation	BPI-5 (average pain)	BPI-4 (least pain)	BPI-3 (worst pain)	BPI-2 (pain distribution)	Assess AEs	Remove Lead	Inspect bandages and Lead exit site	Start Stimulation	Lead Placement	Randomize	Beck Depression Inventory	Remove PNB catheter	Informed Consent	Chart Review/Screening		Visit					
																							×	×	×	×	Screen and Consent						
					×	×	×		×	×	×	×	×	×	×	×						×					Baselin	1					
																					×	×	×						Lead placement (Group 1 only)	2			
										×	×	×	×	×	×		×										1 week PNS	3					
	Data collected from medical record	Data collected from medical record								×	×	×	×	×	×		×										2 weeks PNS	4					
Data co			Data co	Data co	Data co	Data co						×	×	×	×	×	×		×										3 weeks	5			
Data collected from medical record			Data collected from medical record	llected fro	×	×	×	×	×	×	×	×	×	×	×		×		×								4 weeks PNS/1st IPC evaluation	6					
m medi			m medi	Data collected from medical record						×	×	×	×	×	×		×										5 weeks	7					
cal recor	cal recor	cal recor	al record							×	×	×	×	×	×		×										6 weeks	8					
٩	d	ď.	_ a		۵	٩		_						×	×	×	×	×	×		×										7 weeks PNS	9	
										×	×	×	×	×	×	×	×	×	×	×		×	×	×								8 weeks PNS/2nd IPC evaluation	10
						×	×	×	×	×	×	×	×	×	×		×										3 month phone	11					
						×	×	×	×	×	×	×	×	×	×		×										6 month phone	12					
						×	×	×	×	×	×	×	×	×	×		×										12 month phone	13					

Literature Cited

- 1. Richardson et al. A prospective study of factors associated with the presence of Phantom limb pain 6 months after major lower limb amputation in patients with peripheral vascular disease The Journal of Pain Volume 8, Issue 10, October 2007, Pages 793–801.
- 2. Hanley M, et al. Pre-amputation pain and acute pain predict chronic pain after lower extremity amputation The Journal of Pain Vol 8, Issue 2, Feb 2007, pg 102-109.
- 3. Liu SS et al. Prolonged Postoperative Pain in Total Knee and Total Hip Arthoplasty Reg Anesth Pain Med 2012; 37-42.
- 4. Hickey OT et al. Preoperative anxiety and catastrophizing: a systematic review and meta-analysis of the association with chronic postsurgical pain Clin J Pain 2010; 26: 556-560.

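### Chronic pain, a primary outcome, is defined by a range with no visits named, so the end-of-stimulation visit can be counted as chronic pain, and the only named test does not suit its incidence.

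*Combined protocol and SAP*

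**What the plan says.** Section 4.1.2 lists chronic pain as a primary outcome and defines it as follows: "Chronic pain (i.e. pain persisting for more than 2 to 3 months after TFA or TTA surgery will be evaluated". The assessment is made "using BPI questions #3, #4, and #5 as above at follow-up Visits according to the Schedule of Study Procedures", with no visit singled out. The groups are to be compared for "differences in the incidence and severity of chronic pain", but no BPI score or item defines a case.

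Section 6.3 proposes sub-analyses by post-operative phase. After an acute phase of days 1-30, the split is "e.g., 1-3 months), or chronic (e.g. >3 months". Each phase is given as an example. The two-sample t-test is the only test named.

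On timing, Section 5.5.7 places Visit 10 at "approximately 60 days after starting peripheral nerve stimulation (Group 1) or discontinuation of peripheral nerve block (Group 2", with lead removal at that visit. The Schedule in the Appendix labels it "8 weeks PNS/2nd IPC evaluation". For Visits 11-13, Section 5.5.8 says: "Telephone evaluations for both groups occur at approximately 3, 6, and 12 months after study enrollment". Section 5.5 prefers enrolment before surgery but allows it until the nerve block catheter comes out, usually by day 5. Section 3.2 describes enrolment 2 to 7 days after surgery.

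**The concern.** Pain between 2 and 3 months after surgery may be chronic under Section 4.1.2 and is subacute under the Section 6.3 examples. Visit 10 is the scheduled visit that falls in or near that gap, and it closes the stimulation period. If it feeds the chronic outcome, relief obtained while the device is running could be reported as prevention of chronic pain. The protocol's rationale (Section 2.1) is that benefit outlasts the implant, so the two must be kept apart.

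The set of visits and the definition of a case are also open, and both could be settled after the data are seen. Incidence is a proportion, but the plan names only a test of means. With 8 per arm, one reclassified subject moves an arm's incidence by 1/8 = 12.5 percentage points.

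**Working it through.** The plan states no figure to reproduce here. The check is calendar arithmetic, then a comparison of two tests.

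**Conversions.** One month = 365.25/12 = 30.44 days, so 2 months = 60.9 days and 3 months = 91.3 days.

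**Visit 10 = clock start + 56 days (8 weeks, Schedule) or + 60 days (Section 5.5.7).**

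| Group and clock start | Start day after surgery | + 56 | + 60 | Past 2 months? | Past 3 months? |
|---|---|---|---|---|---|
| Group 1, stimulation | 2 (assumed earliest) | 58 | 62 | only at + 60 | no |
| Group 1 | 5 | 61 | 65 | yes | no |
| Group 1 | 7 (latest allowed) | 63 | 67 | yes | no |
| Group 2, end of block | 0 (assumed earliest) | 56 | 60 | no | no |
| Group 2 | 1 | 57 | 61 | only at + 60 | no |
| Group 2 | 5 (usual latest) | 61 | 65 | yes | no |

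Section 1.1 gives 5-7 days after surgery for applying stimulation. On that timing every Group 1 subject passes 2 months by Visit 10 (day 61-67). Group 2 subjects pass it if the catheter stays until day 5, but mostly not after an early or single-shot block. Nobody passes 3 months. Because the clocks differ, the 2-month reading could admit Visit 10 for one arm more often than for the other.

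**State of treatment at Visit 10.** BPI #5 asks about the past week. For a Group 1 subject who uses the device until removal at about 60 days, that week is wholly on stimulation. This assumes that the Schedule, whose table is broken in the available text, marks the BPI pain items at Visit 10, as it appears to.

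**Visit 11 = enrolment day + 91.3.** Enrolment on day -1 gives day 90.3; day 0 gives 91.3; day 2 gives 93.3; day 5 gives 96.3; day 7 gives 98.3. Only the first two fail a strict cut of more than 3 months, by one day or by none.

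**Visits supplying the chronic outcome.** Visits 10-13 (four) on the 2-month reading; Visits 11-13 (three) or 12-13 (two) on the 3-month reading, depending on how Visit 11 is treated.

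**Possible size, as illustration only.** In the chronic-pain series summarised in Section 2.2, the mean reduction in average phantom pain was 81% during stimulation and 47% four weeks after it ended. For residual limb pain the figures were 72% and 42%; for worst pain, 56% at both times. Suppose these carried over and the later effect stayed constant. One on-stimulation visit among four would then give (81 + 3 × 47)/4 = 55.5% instead of 47% for phantom pain, (72 + 3 × 42)/4 = 49.5% instead of 42% for residual limb pain, and no change for worst pain.

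**Test for incidence, example 8/8 versus 4/8.**
- t-test on 0/1 data: the variances are 0 and 8 × 0.25/7 = 0.286, pooled 0.143. The standard error is √(0.143 × 2/8) = 0.189, so t = 0.5/0.189 = 2.65 on 14 df and p is about 0.02.
- Fisher's exact test: the observed table has probability C(8,8) × C(8,4)/C(16,12) = 70/1820 = 0.0385. Its mirror image is equally likely, so the two-sided p = 0.077.

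**The case against.** The strongest reply is that there is no clash of rules. The Section 6.3 phases are examples for sub-analyses, and the upper end of the Section 4.1.2 range agrees with them. If the analyst follows Section 6.3, Visit 10 is subacute and on-stimulation relief stays out of the chronic phase. This stands: the defect is one loose definition, not two binding definitions in conflict. It does not remove the problem, because nothing makes the example split govern the primary outcome.

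A reader might infer that Visit 10 is always chronic under Section 4.1.2 and always on stimulation. The documents support neither. It is chronic only on the 2-month reading, and some timings fall short even then. Stimulation lasts 30 to 60 days and may be stopped at any time, so some Group 1 subjects may be off it by Visit 10, and controls never have it.

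A reader might also infer that the enrolment clock scatters Visit 11 widely around the 3-month cut. The shortfall is at most about a day on the nominal schedule, although the approximate timing of the visit adds to it. The mismatch of clocks matters mainly because a strict cut would then decide which subjects contribute.

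Finally, this is a feasibility pilot with unadjusted p-values. That limits the weight of any test result. However, Section 6.1 intends to report group differences in the primary outcomes and to use the results to design a larger trial, so the definition will be carried forward.

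**Conclusion.** The point holds in a limited form. A primary outcome rests on a range with no named visits, and following Section 4.1.2 as written permits an end-of-stimulation assessment to count as chronic pain. On the usual timings this can apply to most subjects. The outcome may draw on four, three or two visits. The size of any resulting bias cannot be fixed from the documents; the shift of about 8 percentage points in average pain reduction (8.5 for phantom pain, 7.5 for residual limb pain) rests on transferring results from a small chronic-pain series. The mismatch in incidence testing is firmer: the same data can give p about 0.02 or about 0.08 according to the test, in an example chosen for illustration. The calendar results assume stimulation starting on day 2-7, block ending on day 0-5 and enrolment on day -1 to +7. The change should be made, but the finding does not undermine the feasibility aims.

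**What to change.** Use one definition in Sections 4.1.2 and 6.3, stated by visit:

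- The chronic outcome comes from Visits 11, 12 and 13 (3, 6 and 12 months), timed from the date of surgery, each with a stated window. Name Visit 11 as a chronic visit outright. A rule of more than 3 months combined with a visit at exactly 3 months from surgery would put it on the cut.
- Report Visit 10 as the end-of-stimulation (subacute) assessment and not as chronic pain.
- Before any data are examined, fix the BPI item, the pain type (phantom, residual limb or either), the score and the visit that define a case.
- Compare incidence with Fisher's exact test or another exact method; keep the t-test for mean scores.

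The cost is wording and a shift of a few days in the telephone-visit clock. No visits are added.
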